# 6.2.2 Day 1/Randomization Visit

The randomization visit must occur within 30 days after screening/signing of the ICF. Day 1/Randomization procedures are listed in Table 2.

Subjects will be randomized at a 3:1 ratio to the treatment group or the control group. Subjects randomized to the treatment group will proceed to treatment with VOLUX XC (Section 6.2.3) that day, after completion of all of the above procedures. Subjects randomized to the control group will finish the required procedures for the randomization visit and return for a Month 1, 3, and 6 visit during the control period (Section 6.2.4).

#### **6.2.3** Treatment Group

The treatment group will receive treatment at the start of the study and an optional touch-up treatment 1 month later. They will be followed for safety and effectiveness for 12 months after the last treatment (initial or touch-up) with the option for maintenance treatment at Month 12 and an additional 3 months of follow-up.

# 6.2.3.1 Treatment Group: Initial Treatment, Touch-up Treatment, and Follow-up

If the subject is randomized to the treatment group, treatment will be performed on the same day as randomization. In addition, vision assessments (Snellen visual acuity, confrontational visual fields, and ocular motility) will be performed before treatment. The EI will not be present during any of the treatment procedures.

Anesthesia will be administered following the standard practice at each investigational site. The application of ice and topical anesthesia is allowed to reduce injection discomfort. Injectable anesthesia must be limited to the treatment area insertion site only. The TI will use aseptic skin preparation and will administer injections according to the investigational directions for use (IDFU) and Section 9.1.2 of this protocol. The TI will determine the appropriate volume to inject to achieve at least a 1-grade improvement on the ALJDS based on clinical experience.

Approximately 30 minutes after treatment, the TI (or designee) will perform vision assessments. The TI will also evaluate treatment characteristics, including injection ease and product moldability, and will record any AEs.

Subjects will receive instructions on how to evaluate the treatment areas, assess the procedural pain on an 11-point scale, and complete the daily safety diary to record the presence or absence and severity of ISRs starting on the day of treatment and for up to 30 consecutive days after treatment. The diary is to be completed consecutively on a daily basis, until the subject returns for a touch-up/Month 1 Visit (as appropriate) or for 30 consecutive days, whichever is shorter.

Subjects will complete a safety follow-up telephone call 3 days after treatment. If any change to vision is reported during a telephone follow-up or unscheduled phone call, the subject will be asked to come in to the investigational site immediately or will be instructed to receive appropriate care, which may include referral to a retinal specialist. Subjects will return for an office visit 14 days after treatment to undergo 3D facial digital imaging, and the TI (or designee) will perform vision assessments. The subject will not see the blinded EI at the Day 14 visit.

Thirty days after treatment, the subject and TI will discuss the results of the initial treatment. If the TI judges that an ALJDS score improvement of at least 1 grade has not been achieved on each side of the face, it is recommended that the TI perform a touch-up treatment. If the TI judges that an ALJDS score improvement of at least 1 grade has been achieved on each side, a touch-up may be performed if agreed upon by the subject and the TI.

If no touch-up is performed, the subject will exit the initial treatment period and continue with posttreatment follow-up visits and procedures (Section 6.2.3.2), and this visit becomes the Month 1 visit.

If a touch-up is performed, the touch-up treatment visits, procedures, and follow-up are identical to those of initial treatment. The subject will continue with follow-up visits after treatment, as described in Section 6.2.3.2, beginning with the Month 1 follow-up visit, approximately 30 days after touch-up treatment.

Note that before touch-up treatment, women of childbearing potential will take a urine pregnancy test. If the urine test is positive, no touch-up will be performed, and the pregnancy will be followed as described in Section 10.3.

The procedures and evaluations for the treatment period are listed by visit in Table 2.

# **6.2.3.2** Treatment Group: Follow-up/Maintenance Treatment Period

Follow-up visits for safety and effectiveness will occur at 1, 3, 6, 9, and 12 months after initial treatment (or touch-up, if applicable).

After completion of the Month 12 visit, subjects will be offered an optional maintenance treatment. Subjects who decline maintenance treatment will exit the study. Subjects who agree to receive maintenance treatment will be followed for 3 additional months and then exit the study.

The procedures and assessments to be performed at maintenance treatment and at the 4 follow-up visits (Day 3, Day 14, and Months 1 and 3) after maintenance treatment are identical to those after the initial treatment, with the exception that no touch-up will be offered and the product characteristics won't be recorded.

Subjects who are randomized to the treatment group and decide to exit the study at any point before the Month 12 visit must complete the Early Exit Visit procedures in addition to all applicable visit procedures.

The procedures and evaluations to be performed during the follow-up and maintenance treatment periods are listed by visit in Table 3.

# 6.2.4 Control Group

## 6.2.4.1 Control Group: No-treatment Period

Subjects randomized to the control group will complete a 6-month no-treatment control period with office visits at Months 1, 3, and 6 after randomization.

After the Month 6 procedures are complete, subjects will be offered an optional treatment (Section 6.2.4.2). Control group female subjects of childbearing potential who accept optional treatment will take a urine pregnancy test; if the test is positive, the subject will not receive treatment and will be exited from the study. Control subjects who complete the Month 6 procedures, but choose not to have optional treatment, will be considered to have completed the study.

Subjects in the control period who decide to exit the study at any point before the Month 6 Visit must complete the Early Exit Visit procedures in addition to all applicable visit procedures.

The procedures and evaluations for the control group during the no-treatment period are listed by visit in Table 4.

# 6.2.4.2 Control Group: Delayed-Treatment Period

During the delayed-treatment period, subjects will receive optional treatment (initial with optional touch-up) after which they will be followed for effectiveness for 6 months and for safety for 12 months after the last treatment (initial or touch-up).

Control subjects who receive treatment will have the same follow-up visit schedule as the treatment group for 6 months after treatment (initial or initial with touch-up).

Control subjects in the delayed-treatment period who decide to exit the study at any point before the Month 6 Visit must complete the Early Exit Visit procedures in addition to all applicable visit procedures.

The procedures and evaluations for the control group during the delayed-treatment period are listed by visit in Table 5.

### 6.3 Instructions for the Subjects

During each study visit, subjects will be required to remove jewelry (on the neck and/or above the shoulders), make-up, and lipstick, and subjects must be clean-shaven below the subnasale to avoid interference with digital imaging and evaluations of the jaw area.

For 10 days before and 3 days after study treatment administration, it is recommended that subjects avoid using a regimen of anti-coagulation, antiplatelet, or thrombolytic medications; nonsteroidal anti-inflammatory drugs; supplements of Vitamin C or E, garlic, gingko biloba, or ginseng; or other supplements known to increase coagulation time. These precautions are recommended to reduce the risk of posttreatment bleeding or bruising.

Within the first 24 hours after treatment, it is recommended that subjects avoid strenuous exercise, extensive sun or heat exposure, and alcoholic beverages. Exposure to any of the above may cause temporary redness, swelling, and/or itching at the injection sites.

Subjects will also be instructed to contact the TI or his/her research staff to report any unexpected symptoms or to ask questions about the study.

#### 6.4 Unscheduled Visits

An unscheduled visit may occur for safety purposes (eg, if the subject needs follow-up for AEs or ISRs). If an AE is reported during a safety phone call and requires evaluation by the TI in person, an unscheduled visit will be conducted. An unscheduled visit may also occur to repeat facial digital imaging if the images obtained at the scheduled visit are of poor quality. Applicable procedures will be performed and recorded on the eCRF.

# **Early Discontinuation of Subjects**

Each subject reserves the right to withdraw from the study at any time without jeopardy to his/her future medical care. Subjects who discontinue early are to complete applicable study visit procedures and Early Exit Visit procedures. Subjects may also be administratively withdrawn if they do not return for follow-up visits. For any subject who withdraws from the

study, the date and reason for withdrawal will be recorded on the eCRF. If a treatment-related AE is ongoing at the time of withdrawal, the TI will attempt to follow the subject until the AE has been resolved or follow-up is no longer possible. The TI shall ask for the subject's permission to follow his/her status/condition outside the study.

Randomized subjects who withdraw before treatment will not be replaced by another subject. The subject number and associated randomization number of the withdrawn subject will not be reassigned to a different subject.

If a subject fails to return for 1 or more scheduled study visits, the TI (or designee) will attempt to contact the subject to determine and document the reason the subject has failed to return, and to encourage compliance with the study visit schedule.

At regular intervals, the TI (or designee) will record on the eCRF the reasons for which any subjects are discontinued from the study, including subjects who signed the ICF but do not proceed to randomization.

#### 6.6 Withdrawal Criteria

The subject may withdraw at will at any time.

If a subject has a positive urine pregnancy test at the time of the initial or maintenance treatment visit, the subject will not be eligible for treatment and will be withdrawn from the study. If a subject has a positive urine pregnancy test after treatment, she will continue all scheduled visits and non-treatment procedures. The pregnancy will be followed as described in Section 10.3.

In addition, a subject must be withdrawn from the study if he/she:

- receives any dermal filler or fat injection to the chin area
- undergoes facelift or facial reconstructive surgery
- receives treatment with hyaluronidase in the chin area
- changes his/her decision about having photographs taken

A subject may also be withdrawn at the discretion of physician.

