#### 4.4 Permissible and Prohibited Medications/Treatments

#### 4.4.1 Permissible Medications/Treatments

Topical anesthesia may be used during treatment according to routine practice, but it must be limited to the treatment areas only. Examples of permitted topical anesthesia include ice and lidocaine cream. Injectable anesthesia may also be used but must be limited to the treatment area and cannula insertion site.

If a subject is on a regimen of over-the-counter or prescription, oral or topical, anti-wrinkle products below the subnasale, the regimen must have been stable for at least 30 days prior to study enrollment and the subject must continue with the regimen throughout the study.

Otherwise, medications and treatments are permitted with the exception of the restricted medications and treatments described in Section 4.4.2.

The use of any concomitant medication, prescription or over-the-counter, is to be recorded on the subject's electronic case report form (eCRF) at each visit along with the reason the medication is taken.

Therapy considered necessary for the subject's welfare may be given at the discretion of the TI. If the permissibility of a specific medication/treatment is in question, please contact the sponsor.

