#### 4.4.2 Prohibited Medications/Treatments

Subjects must not initiate or be on an existing regimen of anti-coagulant medications (eg, warfarin, clopidogrel) or other medications or substances known to increase coagulation time (eg, aspirin, ibuprofen, herbal supplements) in the 10 days prior to undergoing study device injection and for 3 days afterwards.

During the course of the study, subjects must not:

- Be enrolled in another study and may not receive another investigational product during the course of this study
- Receive permanent facial implants (eg, polymethylmethacrylate, silicone, polytetrafluoroethylene) anywhere in the face or neck
- Undergo fat injections in the malar, chin, or jawline area
- Undergo any piercing or tattooing procedures below the subnasale
- Undergo semi-permanent dermal fillers (eg, calcium hydroxyapatite, poly-L-lactic acid) below the subnasale
- Undergo dermal filler injections in the malar, chin or jawline area
- Undergo mesotherapy or cosmetic treatment (laser, photomodulation, intense pulsed light, radio frequency, dermabrasion, moderate or greater depth chemical peel, liposuction, lipolysis, or other ablative procedures) anywhere in the face or neck
- Receive botulinum toxin injections in the chin, masseter, perioral area, or platysma bands
- Receive deoxycholic acid in the chin, neck, or jawline area

The use of hyaluronidase for aesthetic purposes (eg, to reverse overcorrection) is not permitted.

The decision to administer a prohibited medication/treatment is done with the safety of the study subject as the primary consideration. When possible, Allergan is to be notified before the prohibited medication/treatment is administered.

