#### 11.1.3 Serious Adverse Event

An SAE is defined in accordance with ISO 14155 as an AE that:

- a) led to death,
- b) led to serious deterioration in the health of the subject, that either resulted in
  - 1. A life-threatening illness or injury, or
  - 2. a permanent impairment of a body structure or a body function, or
  - 3. in-patient or prolonged hospitalization, or
  - 4. medical or surgical intervention to prevent life-threatening illness or injury or permanent impairment to a body structure or a body function,
- c) led to fetal distress, fetal death or a congenital abnormality or birth defect

NOTE: Planned hospitalization for a pre-existing condition, or a procedure required by the protocol, without serious deterioration in health, is not considered an SAE. Allergan considers all cancers as SAEs. Abortion is also considered an SAE except for elective abortion of a normal fetus.

See Section 11.4 for procedures for reporting an SAE/serious adverse device effect (SADE).

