# 11.4 Procedures for Reporting an SAE or SADE

All SAEs and SADEs occurring during the study period (from signing ICF) or through the last subject visit are to be immediately reported to an Allergan representative at the fax number/e-mail address listed on the cover page and recorded on the appropriate eCRFs. All subjects with an SAE/SADE must be followed up and the outcomes reported. The TI is to supply Allergan and the IRB with any additional requested information (eg, hospital discharge summary, autopsy reports and terminal medical reports). Allergan will evaluate all SADEs and determine and document in writing whether they meet the definition of a UADE. These shall be reported to all participating TIs, the regulatory authorities, and IRBs as required by national regulations.

In the event of an SAE/SADE, the TI must:

- 1. Notify Allergan immediately by fax/e-mail using the SAE/SADE reporting forms. For the SAE/SADE fax/e-mail number, see the front page of the protocol.
- 2. Obtain and maintain in his/her files all pertinent medical records, information, and medical judgments from colleagues who assisted in the treatment and follow-up of the subject.
- 3. Provide Allergan with a complete, written case history which includes a statement as to whether the event was or was not related to the use of the investigational device.
- 4. Promptly inform the governing IRB of the event, if it is device-related. For other SAEs, notify the governing IRB as required by the IRB, local regulations, and the governing health authorities.

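### Section 6.6 withdraws subjects given chin-area hyaluronidase even for a device complication, which ends the scheduled visits that would find new or delayed events in them

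*Protocol*

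**What the plan says.** Protocol Section 6.6 lists events after which a subject must leave the study. One is that the subject "receives treatment with hyaluronidase in the chin area". No exception is made for medical use.

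Two other sections define what use remains open. Section 4.4.2 says: "The use of hyaluronidase for aesthetic purposes (eg, to reverse overcorrection) is not permitted". Section 4.4.1 says that therapy needed for the subject's welfare "may be given at the discretion of the TI". Hyaluronidase for a complication is therefore allowed, and in the chin it triggers withdrawal.

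Several provisions apply at and after withdrawal:

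- Section 6.5: "Subjects who discontinue early are to complete applicable study visit procedures and Early Exit Visit procedures". The Early Exit column of Tables 2 and 3 lists weight, pregnancy test, concomitant medications and adverse events.
- Section 6.5, for a treatment-related event still ongoing: "the TI will attempt to follow the subject until the AE has been resolved or follow-up is no longer possible". Section 11.3 repeats this.
- Section 11.1.3 counts as serious an event that led to "medical or surgical intervention to prevent life-threatening illness or injury or permanent impairment to a body structure or a body function", and Section 11.4 adds: "All subjects with an SAE/SADE must be followed up and the outcomes reported".
- SAP Section 5.1 shows data collected after exit in listings only.

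Section 6.6 treats one other situation differently. If a pregnancy test is positive after treatment, "she will continue all scheduled visits and non-treatment procedures".

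**The concern.** The rule uses one step, study withdrawal, for two separate decisions: whether to give more product, and whether to keep observing the subject. Hyaluronidase is a sound reason to stop further product and to set later effectiveness scores aside. It is a weaker reason to stop asking about adverse events.

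The subjects concerned have already had a complication that was treated by reversing the product. Section 11.1.1 says that delayed effects such as lumps, nodules, swelling and product dislocation can occasionally appear many months after treatment. Section 6.2 has adverse events solicited at every visit and safety call. Once a subject is withdrawn, nobody is scheduled to ask. At stake is the completeness of the 12-month safety record in a small and clinically informative group. The effectiveness result is not at stake.

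**Working it through.** **1. What follow-up remains after withdrawal, by type of event**

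- The triggering complication: recorded before exit, so it is tabulated.
- A treatment-related event ongoing at exit: followed on an attempt basis, with the subject's permission sought (6.5, 11.3).
- A serious event: follow-up is mandatory (11, 11.4).
- An event that starts after exit: no scheduled contact. Section 11.2 ends collection at the last subject visit. If that means the subject's own last visit, the event is not collected. If it means the last visit of the study, collection is open but no visit or call is scheduled to find the event. Either way, SAP 5.1 would only list it.

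The gap is therefore the last type, together with the weaker follow-up of non-serious complications.

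**2. Which contacts are lost**

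The treatment group is seen at Months 1, 3, 6, 9 and 12 after the last treatment. Delayed-treatment controls are seen at Months 1, 3 and 6 and telephoned at Months 9 and 12.

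- Withdrawal just after Month 1 loses Months 3, 6, 9 and 12.
- Withdrawal just after Month 3 loses Months 6, 9 and 12.
- Withdrawal just after Month 6 loses Months 9 and 12.

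The office visits carry the facial sensation, pronunciation and jaw-function assessments. Any of these done at exit is done once and not repeated.

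**3. The plan's own safety figure**

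Inputs, from Protocol 8.5: at least 144 and 48 randomized, drop-out before treatment of 5% and 15%, incidence 1.5%.

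- Treated: 144 × 0.95 = 136.8 and 48 × 0.85 = 40.8. Rounding each down gives 136 + 40 = 176, as stated.
- Probability of at least one event: 1 − 0.985^176 = 0.930, which agrees with the stated figure of at least 92%.

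**4. How far withdrawal moves that figure**

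The documents give no hyaluronidase rate, so the number lost, k, is an assumption shown over a range. The formula is 1 − 0.985^(176 − k). It treats each withdrawn subject as contributing nothing to the detection of a late event, and all subjects as having equal risk.

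| k assumed lost | Subjects left | Chance of at least one event |
|---|---|---|
| 0 | 176 | 93.0% |
| 1 | 175 | 92.9% |
| 3 | 173 | 92.7% |
| 5 | 171 | 92.5% |
| 9 | 167 | 92.0% |

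Even 9 subjects, 9/176 = 5.1%, cost one percentage point.

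**5. Whether the loss is necessary**

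The pregnancy provision shows that Section 6.6 can stop treatment without stopping visits. The hyaluronidase criterion also names only the chin, while product is injected in the pre- and post-jowl areas, the marionette lines and the angle of the mandible as well (9.1.2). A subject given hyaluronidase at the mandible angle is not required to leave. Follow-up after reversal is thus already possible under this protocol.

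**The case against.** The case for leaving the rule alone has real content.

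- **The gravest events are covered in other ways.** Vision-related events go to the sponsor within 24 hours and to FDA within 10 working days (11.3). A vascular embolic event leading to necrosis, vision loss or stroke suspends treatment at the site (10.4). Subjects are told to report unexpected symptoms (6.3). This narrows the gap but leaves no scheduled contact for delayed, non-serious events.
- **Recurrence would change little.** SAP 5.6.3 counts a participant once per preferred term at greatest severity, so a repeat of the recorded complication alters incidence only if it is worse. This stands. The loss concerns different terms, greater severity and total event counts.
- **The product has been altered.** After hyaluronidase, later sensation, jaw-function and adverse event data no longer describe the intact device. This is a fair reason to flag the data, but it does not require that collection end.
- **The pregnancy parallel is partial.** Pregnancy leaves the device in place, and the same paragraph withdraws a subject who tests positive at the initial or maintenance treatment visit. The parallel shows only that visits can continue when treatment stops.
- **Few subjects are involved.** In the earlier study most treatment-related events needed no treatment (2.2), and the rule names only the chin. This stands and limits the weight of the point.

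A reader might infer that complications needing reversal drop out of the safety results. They do not: the triggering event is tabulated, and serious events must be followed to an outcome. A reader might also suppose that late events cluster in the withdrawn subjects. If they would have had a quarter of all late events, detection would be 1 − (1 − 0.015 × 0.75)^176 = 86.3%. The documents give no basis for that share or any other, so it cannot be used to enlarge the point.

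**Conclusion.** The concern holds as a limited design point. Section 6.6 ends scheduled safety observation in subjects whose chin-area complication was treated with hyaluronidase, and the remaining provisions cover known events but do not look for new ones. The number of subjects is unknown and likely small. Overall detection stays at about 93% for a 1.5% event, and at 92% or more with up to 9 subjects lost under the equal-risk assumption. The primary conclusion is unaffected.

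The documents do not support reading this as a material bias in the safety profile, or as a bar on treating complications, since Section 4.4.1 leaves necessary therapy to the treating investigator. The point is worth acting on because the change is inexpensive and keeps follow-up in subjects known to have had a complication.

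**What to change.** **Protocol 6.6.** State that hyaluronidase given for an adverse event stops further study treatment, and that the subject continues all scheduled safety visits and calls. Whether and how it is used stays with the treating physician. These data would then fall before study exit, inside the treated or maintenance period of SAP Table 5-1, and would be tabulated without a change to the post-exit rule in SAP 5.1.

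**SAP.** Add one sentence: ALJDS and other effectiveness scores taken after hyaluronidase are not used and are handled as missing. Retained subjects will reach Month 6, and SAP 6.4.1.1 would otherwise take their scores into the analysis windows. Under the current rule withdrawal already leaves later scores missing, so the primary analysis stays as planned.

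**Reporting.** Flag safety data collected after hyaluronidase, since they reflect a partly reversed product.

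**Cost.** One protocol amendment with IRB approval (12.2), one SAP sentence, and a few already scheduled visits or calls for a few subjects.
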